2.2 Secondary Objectives

- To measure the risk of leaving tumor cells in the prostate after LEAD RT by obtaining serial post-RT MRI's (3 months and 9 months, and within 2 months of the post-treatment prostate biopsy).
- To quantify biomarker expression in different prostate tumor regions, comparing specifically the multiparametric suspicious and unsuspecting regions.
- To determine the proportion of study patients with positive prostate biopsies at 2-2.5 years after completion of therapy as a preliminary indication of the efficacy.
- To report failure-free (biochemical and clinical progression) and overall survival.
- To assess Health-Related Quality of Life (HRQOL) in the study patients.

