4.2 Assessment of Protocol Eligibility and Enrollment

Patients who have a suspicious lesion (or lesions) on multiparametric MRI that involves <33% of the prostate will be eligible. A suspicious lesion is defined as distinct early enhancement on DCE-MRI or significant water motion restriction by DWI reflected as a point value of <1000 on an Apparent Diffusion Coefficient (ADC) map. Thus, patients who unable to receive contrast for the MRI are still eligible. The DCE-MRI would be expected to show early washin and delayed washout. For DCE-MRI early enhancing anterior lesions in the transition zone that meet these criteria, there is also the requirement for a point value of ≤ 1000 on the ADC map in that region or a high choline + creatinine to citrate ratio (≥ 0.9 ratio) on MR spectroscopy. MRS is being added to our current standard multiparametric assessment algorithm. Eligible patients will be screened by the treating physicians and dedicated protocol nursing staff for fulfillment of eligibility criteria. If the patient is deemed eligible, protocol consent will then be obtained. The treating protocol physician will explain the risks and procedures to the patient, along with the Clinical Research Coordinator. The patient will be entered into the

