4.8 LEAD Dose Distribution, Planning and Constraints

Dose Pipe Distribution: 12-14 Gy dose pipes on day 1.

The LEAD dose distribution may be planned and delivered by the Cyberknife or a standard LINAC, if the dose distributions are deemed acceptable. The LEAD RT dose plan will involve the placement of 1 to 3 dose pipes of 7.5 mm diameter the length of the multiparametric MRI-defined GTV volume with roughly 50 non-coplanar focused beams for each dose cylinder planned using the Cyberknife. The GTV will include the early phase contrast enhancing lesion on DCE-MRI, considered with the abnormality on T2-weighted imaging and for transition zone lesion the ADC map and/or the MRS choline+creatine to citrate ratio. The LEAD RT region(s) will be positioned as close to the center of GTV region(s) as possible (should be positioned ≥ 2 mm from the rectum to avoid excessive dose to the rectum).

LEAD Planning: To provoke a bystander effect, we propose to deliver 1-3 LEAD dose cylinders in the prostate gland, no more than 2 per side. Ideally, the GTVs will be covered by the 10 Gy isodose envelop, with the maximum prescribed dose ranging from 12 Gy to 14 Gy. The separation between the dose cylinders should be such that the dose between should decrease to 20-30% of the maximum dose, while the dose to critical structures such as rectum, bladder and urethra are controlled under known tolerance constraints.⁹⁰

[figure not shown]

Figure 7. Theoretical treatment model generating a LEAD dose distribution in 3-D using a robotic radiosurgery system. Two high dose vertexes are simulated in parallel to one another. The diameter of each one is 7.5 mm and its length (up to 20 mm) is determined by the size of the tumor.

Techniques that can be applied to achieve such dose distribution include non-coplanar focused photon beam with a Cyberknife or an aperture modulated arc (AMAT) with a DMLC linear accelerator. Image-guidance and

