14.2 Analysis Plan

Study findings will include descriptive statistics summarizing patient baseline characteristics, RT planning parameters and treatment received⁹⁴. A detailed safety profile will be provided consisting of lists and tabulations of all adverse events indicating type, grade, attribution to treatment and time of onset relative to treatment according to CTCAE standards. This will be done separately for acute and late toxicity (see Section 9.1). Patient level summaries will include worst grade toxicity and the number and duration of treatment delays attributable to toxicity.

Feasibility will be assessed by reporting the proportion of enrolled patients who are administered LEAD dose following successful MRI-guided planning and corresponding 95% confidence interval (CI) using the exact binomial method. The same method will be used to estimate the two-year positive biopsy rate defined as the proportion of positive biopsy findings among patients without clinical or biochemical failure two years after completing study treatment.

Clinical outcome will be further assessed by estimating the rate of biochemical failure, as defined in Section 9.1, using the method of cumulative incidence allowing for competing risk of death without biochemical failure. Biochemical failure free survival will be estimated by the Kaplan Meier method. Similar analysis will be provided for the combined rate of biochemical and clinical failure (cumulative incidence) and failure free survival (Kaplan Meier). Although death of study patients during the planned follow up period is expected to be rare and not attributable to prostate cancer, we include these survival endpoints (biochemical failure-free, failure-free, and overall survival) for completeness.

We will summarize the scores of QOL assessments with descriptive statistics and apply mixed effects modeling to evaluate changes over time.

Finally, to the extent permitted by available data from baseline biopsies, exploratory analysis will be performed to investigate the relationship between the level of biomarker expression in tumor tissue within vs. outside the DCE-MRI determined region and the correlation between these measures and Gleason score. Analysis of the sequential imaging studies will correlate the presence/absence of DCE enhancing area and its volume with biopsy positivity at 2 – 2.5 years. We will attempt to establish the ability of MRI for early assessment of RT outcome.

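### The biomarker comparison in section 14.2 is defined by DCE-MRI alone, although its objective is multiparametric and ADC-only and non-contrast lesions are eligible

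*Combined protocol and SAP*

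**What the plan says.** **Analysis.** Section 14.2 plans an exploratory comparison of biomarker expression in tumor "within vs. outside the DCE-MRI determined region", carried out "to the extent permitted by available data from baseline biopsies". It also plans to "correlate the presence/absence of DCE enhancing area and its volume with biopsy positivity at 2 – 2.5 years". It names no ADC alternative and gives no rule for scans without contrast.

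**Objective.** Section 2.2 sets out to quantify expression in different tumor regions, "comparing specifically the multiparametric suspicious and unsuspecting regions".

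**Eligibility.** Section 4.2 defines a suspicious lesion as "distinct early enhancement on DCE-MRI or significant water motion restriction by DWI", and adds that "patients who unable to receive contrast for the MRI are still eligible". Inclusion criterion I.b in 3.1, exclusion criterion F in 3.2 and section 4.1 agree. Follow-up MRI (5.3) uses contrast only where possible.

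**Target volume.** The Schema accepts either DCE enhancement or ADC restriction as the basis of the GTV. Section 4.10 refers to the multiparametric lesion. Section 4.8 says "The GTV will include the early phase contrast enhancing lesion on DCE-MRI", read together with T2 and, for transition zone lesions, the ADC map and/or spectroscopy.

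**The concern.** The region that decides which tissue counts as inside is narrower than the region that makes a man eligible, that receives LEAD, and that the objective names. Two kinds of eligible patient do not fit:

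- A man scanned without contrast has no DCE region, so his tissue is neither inside nor outside.
- A man who had contrast but whose lesion is restricted on ADC without early enhancement has an index lesion that lies, by the wording of 14.2, outside.

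The first costs tissue in a study of 25 men. The second puts index-lesion tissue into the comparison group, which would normally pull the two groups together.

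The sequential imaging analysis has a related weakness. A follow-up scan with no DCE area may mean that nothing enhanced, or that no contrast was given. If the second is coded as absence, the correlation with biopsy result mixes a finding with a missing measurement.

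**Working it through.** The plan states no sample size, power or precision for these analyses, so there is no figure to reproduce. The main check is to set the definitions side by side.

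| Place | Basis of the region |
|---|---|
| 2.2, biomarker objective | multiparametric |
| 4.2, eligibility | DCE or DWI/ADC; no contrast accepted |
| Schema, GTV | DCE or ADC |
| 4.10, GTV | multiparametric |
| 4.8, GTV | DCE lesion with T2; ADC and/or spectroscopy added for transition zone |
| 14.2, biomarker regions | DCE |
| 14.2, imaging predictor | DCE area, presence and volume |

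Applying 14.2 to each eligible case:

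1. Contrast given, lesion enhances: tumor from the lesion is inside. No problem.
2. Contrast given, lesion is ADC-only: tumor from the treated target is outside. If this is the man's only lesion, he has no inside tissue.
3. No contrast, lesion qualifies on ADC: no DCE region exists, so the man is unclassifiable.

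Cases 2 and 3 are admitted by 4.2, so the mismatch follows from the text.

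**Size, illustrative only.** The documents give no share f of such men or lesions. Assume f between 4% and 40%.

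- *Drop-out (case 3).* Men remaining = 25 × (1 − f). The 25 is an upper limit, because the baseline biopsy is optional (Schema, 4.3).
- *Mislabelling (case 2).* Assume one target and one non-target tumor core per man, equal weights, and ADC-only lesions with the same mean as enhancing ones. With target mean T and non-target mean N, the outside mean is (N + f·T)/(1 + f). The observed difference is T − (N + f·T)/(1 + f) = (T − N)/(1 + f).
- *Chance of at least one such man among 25*, if men are independent: 1 − (1 − f)^25.

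| Assumed f | Men left, at most | Share of true difference seen | Chance of at least one |
|---|---|---|---|
| 4% | 24 | 1/1.04 = 96% | 64% |
| 10% | 22.5 | 1/1.10 = 91% | 93% |
| 20% | 20 | 1/1.20 = 83% | above 99% |
| 40% | 15 | 1/1.40 = 71% | above 99% |

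The middle columns are alternatives for different patients and should not be combined. If ADC-only lesions express the marker less than enhancing ones, the shrinkage is smaller; if they resemble non-target tumor, it vanishes.

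**The case against.** The best defense is that the DCE focus is deliberate. The second hypothesis and section 1.1 propose that the dominant areas are angiogenic and appear hypervascular on MRI. Section 1.4.3 links DCE to hypervascularity, and 1.4.7.2 describes DCE delineation software with a threshold chosen for this project. A DCE contrast is a fair test of that idea. This stands as a reason to keep the contrast, but it cannot classify a man without contrast, and it is narrower than the objective in 2.2.

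The analysis is also exploratory and limited to available biopsies, and feasibility and toxicity do not depend on the DCE region. That stands and limits the importance of the point.

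For follow-up imaging, a reader might infer that DCE should give way to any multiparametric lesion. The documents do not support this. Their ADC threshold is given for eligibility and planning, not for irradiated prostate. Section 1.4.6 warns that radiotherapy itself lowers T2 signal, and no section says that follow-up lesions are contoured.

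A reader might also infer from 4.8 that the GTV rests on DCE alone. It does not: T2 is considered for all lesions, and ADC and/or spectroscopy for transition zone lesions. What remains is that 4.8 gives no explicit route for an ADC-only or non-contrast peripheral-zone lesion, which the Schema and 4.10 would cover.

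**Conclusion.** The point holds for the biomarker comparison: its stated rule does not match its own objective or the patients admitted. It is a low-cost correction to an exploratory analysis, and no primary endpoint is affected.

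The size is unknown. The table rests on an assumed share, one target and one non-target core per man, and equal expression in ADC-only and enhancing lesions; none of these is in the documents. A reader might infer a fixed loss of 1/25 = 4% per non-contrast man. That is not supported for the biomarker analysis, whose denominator is the unknown number of men who accept biopsy and have usable tumor tissue.

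Nor do the documents state that non-contrast men will be dropped or ADC-only targets relabelled. These outcomes follow from applying the wording literally, and no handling rule is given. It would also go too far to say that the objective is not analyzed at all: it is analyzed through a narrower region.

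For sequential imaging the DCE measure can stay; the weakness is limited to scans without contrast. The GTV descriptions are a separate inconsistency between the Schema, 4.8 and 4.10.

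**What to change.** 1. In 14.2, define the inside region for the biomarker comparison as the baseline multiparametric lesion (DCE or ADC) used for LEAD planning.
2. Record for each lesion which sequence defined it: DCE, ADC or both.
3. Keep the DCE-only contrast as a secondary analysis among men who had contrast.
4. In the sequential imaging analysis, keep the presence and volume of the DCE area, restrict it to scans done with contrast, and report how many scans are left out. A scan without contrast is then missing, not negative.
5. Reconcile the GTV text in the Schema, 4.8 and 4.10 so that they treat ADC-only and non-contrast peripheral-zone lesions consistently. This review takes no position on which description is right.

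Items 1 to 4 need a wording change in 14.2, one field per lesion and a contrast flag per scan. No new baseline imaging is needed, because 15.4 already lists pre-treatment multiparametric tumor size and location among the source documents. Every eligible man would then have an inside region, and the loss of data would be confined to declined biopsies and samples without usable tumor.

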14.3 Stratification Factors
N/A

14.4 Interim Monitoring

We propose the following guidelines for the Sylvester Data and Safety monitoring Committee (DSMC) (see also Appendix III) in its review of accumulating data on toxicity and feasibility of study treatment. The proposed guidelines were developed using Bayesian methods, which can be applied at any stage of enrollment without advance specification of the number of interim analyses to be performed, or the number of patients evaluable for toxicity, or response, at the time such assessments are made.^{95,96}

Under the Bayesian method, we assign a prior probability (level of belief at the start of the trial) to a range of possible values for the true toxicity rate, and likewise for the true feasibility rate. As data on treated patients become available, each of these probability

Number of Patients With acute treatment Related Grade 3+ GI/GU Toxicity	Total Patients Evaluated	Observed Rate
2	3 to 6	≥33% (2 of 6)
3	7 of 11	≥27% (3 of 11)
4	12 to 16	≥25% (4 of 16)
7	17 to 25	≥25% (7 of 25)

distributions is revised and the resulting posterior probability becomes the basis for recommending either early termination or continuation of the study. In the sections that follow, we provide specific stopping guidelines based on posterior probabilities for monitoring toxicity and efficacy over the course of this trial. Underlying assumptions for the prior distributions are also presented.

Stopping rules for safety: The following early stopping guidelines, which are based on a Bayesian method, will be

applied to ensure safety of this Phase I trial. Safety monitoring will be based on the occurrence of treatment related (possible, probable, or definite) grade 3 or higher GI or GU toxicity occurring during study treatment or within 30 days of treatment completion. Early stopping (suspension and possibly termination) will be considered if there is evidence that the proportion of patients experiencing such toxicity exceeds 15%. Specifically, we suggest as a guideline for early termination a posterior probability of 80% or higher that the rate of grade 3 or higher GI/GU toxicity exceeds 15%. **Table 2** shows specific instances where this guideline is met, thus suggesting early termination due to evidence of excessive toxicity.

As an additional safeguard, the first three patients enrolled on study will be observed for 30 days following treatment completion of the third patient before enrollment is continued (fourth patient). If two or three of the first three study patients have grade 3 or higher GI/GU toxicity within 30 days of treatment completion, enrollment will be suspended pending DSMC review. If none or one of the first three patients enrolled on study have grade 3 or higher GI/GU toxicity

within 30 days of treatment completion, enrollment will continue without restriction on the interval between successive enrollments.

Posterior probabilities used to derive the preceding table are calculated under a prior beta distribution with parameters $\beta_1 = 0.2$ and $\beta_2 = 1.8$, which corresponds to an expected rate of 15% based on prior information roughly equivalent to having studied 2 patients^{96,97}. Furthermore, this prior distribution assigns a small a priori chance (32%) to the possibility that the true rate of unacceptable toxicity is 15% or greater.

Table 3. Stopping Rules For Lack of Feasibility

Number of Patients ineligible For LEAD	Total Patients enrolled and completed CT simulation	Observed LEAD ineligibility rate
2	3	67%
3	4 to 6	≥50% (3 of 6)
4	7 to 10	≥40% (4 of 10)
5	11 to 13	≥38% (5 of 13)
6	14 to 17	≥35% (6 of 17)
9	18 to 25	≥35% (9 of 25)

Stopping rules for lack of feasibility

Similarly, for purposes of monitoring the feasibility of delivering LEAD RT, we consider the proportion of patients enrolled on study for whom it is not possible to deliver LEAD RT as determined from CT/MRI simulation and planning, referred to as the *LEAD ineligibility rate*. The LEAD treatment will not be delivered if the summed dose of LEAD and conventional treatment to critical structures exceeds tolerance. Early stopping due to infeasibility of the proposed study treatment will be considered if there is evidence that the rate of LEAD ineligibility exceeds

20%. Specifically, we suggest as a guideline for early termination a posterior probability of 90% or higher that the rate of unacceptable toxicity exceeds 20%. **Table 3** shows specific instances where this guideline is met, thus suggesting early termination due to early evidence of LEAD infeasibility.

Posterior probabilities used to derive the preceding table are calculated under a prior beta distribution with parameters $\beta_1 = 0.4$ and $\beta_2 = 1.6$, which corresponds to an expected rate of 20% based on prior information roughly equivalent to having studied 2 patients. Furthermore, this prior distribution assigns a small a priori chance (36%) to the possibility that the true rate of unacceptable toxicity is 20% or greater.

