14.0 STATISTICAL CONSIDERATIONS

14.1 Sample Size/Accrual Rate

Twenty five (25) patients will be enrolled over a two-year period, subject to early stopping rules for safety (grade 3 or higher treatment-related acute GU/GI toxicity) and feasibility (LEAD eligibility). Study size is intended to provide initial evidence of safety and feasibility of the proposed treatment as a basis for planning Phase II efficacy trial.

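### The last row of the toxicity stopping table requires 7 events in 17 to 25 patients, but the plan's own 80% rule is already met at 5 events (17 to 21 patients) and 6 events (22 to 25)

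*Combined protocol and SAP*

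**What the plan says.** Section 14.1 plans 25 patients. Section 14.4 monitors treatment-related "grade 3 or higher GI or GU toxicity occurring during study treatment or within 30 days of treatment completion". Its guideline for early termination is "a posterior probability of 80% or higher that the rate of grade 3 or higher GI/GU toxicity exceeds 15"%, and Table 2 is presented as showing where that guideline is met.

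Table 2 has four rows: 2 events in 3 to 6 patients, 3 in 7 to 11, 4 in 12 to 16, and 7 in 17 to 25. The last two rows, in the order count, patients evaluated and observed rate, read "4 12 to 16 ≥25% (4 of 16") and "7 17 to 25 ≥25% (7 of 25").

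The table is said to come from a beta prior with "parameters $\beta_1 = 0.2$ and $\beta_2 = 1.8$, which corresponds to an expected rate of 15"%. The weight of that prior is described as "based on prior information roughly equivalent to having studied 2 patients". The section adds that "this prior distribution assigns a small a priori chance (32%) to the possibility that the true rate of unacceptable toxicity is 15% or greater".

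**The concern.** The required count rises by one from row to row (2, 3, 4) and then jumps to 7 for the last nine patients. A fixed posterior threshold cannot behave like that. Table 2 would suggest stopping at 4 of 16 (25%) and yet let 5 of 20 (also 25%) or 6 of 22 (27%) pass.

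Toxicity is part of the primary objective (Section 2.1), and Table 2 is the form of the rule that the monitoring committee can use without computing anything. If the last row is too high, the error runs in the permissive direction: late in accrual, enrolment continues at counts that the plan's own criterion calls excessive.

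**Working it through.** **Inputs, all from Section 14.4.** Reference rate 15%; posterior threshold 80%; prior parameters summing to 2. Two priors were used because the printed one does not match its own description:

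- Beta(0.2, 1.8), as printed: mean 0.2/2 = 10%, P(rate > 15%) = 21.6%.
- Beta(0.3, 1.7): mean 0.3/2 = 15%, P(rate > 15%) = 32.3%. This matches the stated 15% and 32%.

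**Formula.** With x events in n patients and prior Beta(a, b), the posterior is Beta(a + x, b + n − x). The stopping count at n is the smallest x with P(rate > 0.15) ≥ 0.80.

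**Reproducing rows 1 to 3.** Under Beta(0.3, 1.7) each row is exactly the minimum count, and each range ends where it should:

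| Last n in row | Posterior | Same count at n + 1 |
|---|---|---|
| 2 of 6 | 80.1% | 2 of 7: 74.9% |
| 3 of 11 | 80.1% | 3 of 12: 76.2% |
| 4 of 16 | 80.9% | 4 of 17: 77.8% |

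Under the printed prior the upper end of each row just misses (77.5%, 78.1%, 79.2%). The table was therefore evidently built with Beta(0.3, 1.7).

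**Row 4.** The same calculation continued:

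| Events / patients | Beta(0.2, 1.8) | Beta(0.3, 1.7) | 80% rule met? | Printed table |
|---|---|---|---|---|
| 4 / 17 | 75.9% | 77.8% | no | continue |
| 5 / 17 | 90.1% | 91.0% | yes | continue |
| 5 / 18 | 88.0% | 89.0% | yes | continue |
| 5 / 20 | 83.2% | 84.5% | yes | continue |
| 5 / 21 | 80.5% | 82.0% | yes | continue |
| 5 / 22 | 77.7% | 79.3% | no | continue |
| 6 / 22 | 90.0% | 90.9% | yes | continue |
| 6 / 25 | 84.0% | 85.2% | yes | continue |
| 7 / 17 | 99.1% | 99.2% | yes | stop |
| 7 / 25 | 93.0% | 93.6% | yes | stop |

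The minimum is 5 for n = 17 to 21 and 6 for n = 22 to 25 under both priors. Thresholds of 80%, 85%, 90% and 95% were tried, and none gives 7 across 17 to 25. The rate label fails too: 7/25 = 28%, not 25%.

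**Effect on stopping.** Exact recursion over the binomial paths, with a look after every patient from n = 3, rows 1 to 3 as printed, and then either 7 throughout (printed) or 5 and 6 (rule):

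| True rate | No stop by n = 16 | First stop at n = 17–25: printed / rule | Same, given no stop by n = 16 | Overall stopping: printed / rule |
|---|---|---|---|---|
| 15% | 65.7% | 0.6% / 4.1% | 0.9% / 6.2% | 34.9% / 38.3% |
| 25% | 29.9% | 2.6% / 8.3% | 8.7% / 27.7% | 72.7% / 78.4% |
| 30% | 17.4% | 3.0% / 7.3% | 17.0% / 42.0% | 85.6% / 89.9% |

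The conditional column is the late-stop probability divided by the probability of reaching n = 16 without a stop, for example 2.60/29.92 = 8.7%.

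**The case against.** **The row is true as far as it goes.** Seven events in 17 to 25 patients do satisfy the 80% guideline, the table claims only to show instances, and the guideline in the text still stands for a committee that computes the posterior. This is correct. But rows 1 to 3 are minimum counts and readers will take row 4 the same way. At 5 of 20, the text suggests stopping and the table suggests continuing.

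**The most striking counts cannot occur with a look after every patient.** Passing n = 16 then requires at most 3 events, so at most 4 are possible at n = 17. This also stands: under that schedule the first discrepant count is 5 of 18. Section 14.4 does not fix the number of looks, however, and Appendix III describes periodic review of toxicity, so 5 or 6 of 17 can arise when looks are sparser.

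**The overall effect is modest.** Most toxic scenarios stop on rows 1 to 3, and the unconditional gain is 4 to 6 percentage points at true rates of 25% and 30%. This is right, and the conditional figures should be read with it.

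**Enrolment may be nearly over when the row applies.** A patient is evaluable about 11.8 weeks after starting (7.5 weeks of radiotherapy plus 30 days). At 25 patients in 104 weeks with uniform accrual, about 11.8 × 25/104 = 2.8 more will have started by then. When 22 have been evaluated, accrual is close to complete, so the practical effect falls mainly at 18 to 21 evaluated patients. That narrows the consequence but does not make the row correct.

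**Conclusion.** The concern holds. The last row of Table 2 contradicts the rule it is meant to express, and it does so under either reading of the prior, so the separate inconsistency in the printed prior neither explains nor rescues it. The rule itself is sound; the fault lies in the row. The required count is too high by two for 17 to 21 patients and by one for 22 to 25, and the rate label is wrong.

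The loss of protection is small over the whole trial: overall stopping falls from 78.4% to 72.7% at a true rate of 25%, and from 89.9% to 85.6% at 30%. It is large in the stretch the row governs, where late stopping falls to less than half of what the rule gives. These probabilities assume a look after every patient from the third with outcomes known at each look; the minimum counts need no such assumption. Because this is a safety boundary and the error is permissive, it must be corrected.

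**What to change.** Replace the last row of Table 2 with two rows:

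- 5 events, 17 to 21 patients, observed rate ≥24% (5 of 21 = 23.8%)
- 6 events, 22 to 25 patients, observed rate ≥24% (6 of 25 = 24.0%)

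Leave the 80%/15% rule and rows 1 to 3 as they are.

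Two related errors in Section 14.4 should be corrected at the same time, although this fix does not depend on them. The printed prior parameters should be reconciled with the stated 15% mean and 32% tail; Beta(0.3, 1.7) fits both and also rows 1 to 3. The last row of Table 3 makes the same kind of jump: it prints 9 for 18 to 25 patients, whereas its 90% rule under the stated Beta(0.4, 1.6) prior is met at 7 for 18 to 21 and 8 for 22 to 25.

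The cost is a table edit and a slightly higher chance of a late pause when toxicity is acceptable: at a true rate of 15%, overall stopping rises from 34.9% to 38.3%. The stated rule already implies that.
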